## Motor Testing

1. *Purdue Peg Board Task*: The Purdue Pegboard measures unimanual motor dexterity. The test consists of two parts: 1) placing pins in a column of holes and

2) an assembly task using three components (pin, washer, collar). The participant is asked to place as many items as possible in 30 or 60 seconds, respectively.

2. *Nine Hole Peg Board Task*: A standard dexterity assessment, this task asks participants to place and remove pegs on a nine-hole pegboard as quickly as possible.
3. *Pinch and Grip Strength*: FDI and hand strength will be assessed using standard dynamometer (JAMAR) squeeze tests.
4. *Coin rotation task*: Another dexterity assessment, this task asks participants to rotate a coin (U.S. quarter) as quickly as possible for 20 rotations.
5. *Halstead finger tapping*: The Halstead finger tapping test is a standard test for testing psychomotor speed. The participant is asked to press a lever attached to a counter as many times as possible in 10 second trials.

## **MRI**

*Structural Imaging*: High-resolution T1-weighted and T2-weighted structural imaging will be obtained to assess Tissue Integrity Gradation via T2w T1w Ratio (TIGR) and will also serve as an anatomical reference for functional data. We will also collect Diffusion Weighted Images (DWI) to assess white matter integrity. During this time participants are given the option to view a movie to alleviate potential boredom.

*Metabolic Imaging*: Cerebral Blood Flow will be assessed with MRI scans that separate pure blood signal from surrounding tissue (e.g. pCASL or VSASL). If arterial transit time is a factor based on the imaging sequence, we will remove this confound by either using longer post-labeling delays or measuring multiple post-labeling delays. For a few minutes of scanning, we will ask participants to breath via a mask air richer in CO2 than normal atmospheric air (5-8%). CO2 will be administered by study staff. The CO2 reactivity procedures are tolerated by normal, elderly subjects and patients with neurological diseases such as history of strokes and have been performed numerous times in our imaging center without complications.

*Functional Imaging*: Integrity of functional brain networks will be assessed while the participant is lying still inside the scanner, and Blood Oxygen Level Dependent (BOLD) fMRI signals are collected. Alternatively, the participant may be asked to perform either a language task or motor task while BOLD fMRI data is collected, depending on the question of interest.

*Magnetic Resonance Spectroscopy*: Magnetic resonance spectroscopy will be performed on selected large (e.g. 4-27 mL) voxels to estimate quantities of various neurochemicals.  $\gamma$ -aminobutyric acid (GABA) and glutamate are the primary neurochemicals of interest, though other substances (e.g., N-acetylaspartate, creatine) may also be measured.

Regions of interest include, but are not limited to, the DMN (medial and lateral structures), motor cortex (M1), inferior frontal gyrus, and fusiform gyrus.

[figure not shown]
No exogenous contrast agent will be used during any of the MRI and MRS protocols.

### **FMRI Tasks**

For the verbal fluency task in the scanner, participants will see different categories at the center of a video screen while in the scanner. The participant's task will be to generate different exemplars of the respective category (semantic) or as many words that begin with a particular letter (phonemic). The fMRI fluency task will consist of two blocked conditions of category or phonemic generation, which will alternate with a control condition (reading the word "rest" aloud). A baseline condition will be used to control for activity associated with (a) basic visual processing, (b) articulation and, (c) hearing of the subject's own voice. A total of 4 blocks for each condition will be collected (i.e., 40 trials for category and phonemic fluency).

For the verbal working memory task, both memory and control trials will be presented in a pseudorandom order across five runs, each containing 14 trials. This will produce 35 memory trials and 35 control trials over the course of the experiment. For a memory trial, the first slide will depict a single lexical target. Participants will be instructed to read and remember this "target word" with the knowledge that sometime later they will be shown a second word, referred to here as the "decision word". Upon seeing the decision word, participants will initiate a button press indicating whether the target and decision words are semantically related. The time in-between presentation of the target and decision words will be filled with additional slides, referred to here as "distractor slides". Each distractor slide will present two words. Participants will be asked to make a semantic relatedness judgment for each of these distractor word pairs. A single memory trial is depicted in the diagram below. The timing parameters will be identical for both the memory and control trials. Specifically, slides 1-4 will present for 2 seconds each, and slide 5 will be shown for 4 seconds. A 10-second blank screen inter-trial interval will be used to allow hemodynamic response recovery.

Diagram of the experimental task, showing a single memory trial and a single control trial. Each trial will last 12 seconds for both task conditions (control & memory) and will be separated from the subsequent trial by a 10-second blank screen. Color-coding indicates the phases delineated for the functional task activation analysis.

The fMRI acquisition for semantic will follow protocols currently utilized in the investigator's laboratory and therefore will employ a sparse-temporal sampling design in which the response is assessed in the scanner during an off-phase, and the hemodynamic response is acquired after a short time delay; thereby movement artifacts due to the articulation process are avoided. Since the working memory task involves no overt speech, a continuous sampling acquisition will be used to allow for temporal resolution of the different phases of the working memory task. A T2\*-weighted FastField Echo, Echo-Planer-Imaging (FFE-EPI) sequence utilizing a parallel imaging technique will be used. Prior to the first scan, a training session outside of the scanner will be performed to familiarize the participants with experimental tasks. Participants will be scanned prior to and following the 12-week intervention. Additionally, for fluency both semantic and phonemic stimulus presentation will be different but equalized for difficulty from pre to post.

The MRI/fMRI will be conducted at Emory University Hospital (EUH). EUH houses a 3 T Siemens Trio scanner with the total imaging matrix (TIM) suite. The scanner is equipped with a 32-channel Siemens head coil, which allows for rapid acquisition of high-resolution functional images (e.g., 2 X 2 X 2 mm voxels with a whole brain acquisition every second). It has the latest Siemens VB17 software and has a number of advanced Siemens product sequences including Blood Oxygenation Level Dependent (BOLD) imaging and in-line analysis suite with 3D PACE real time motion correction.

### Blood Draws and Biomarker Evaluation

Whole blood will be collected, by a certified phlebotomist, through one venous port venipuncture or peripheral venous line into standard plasma tubes or serum separator tubes (~40 ml per visit). Following collection, tubes will be transferred in accordance with blood borne pathogens training standards to the Molecular Core facility of the Atlanta VAHCS. Serum and plasma aliquots will be analyzed for biomarkers (e.g., BDNF) by ELISA, western immunoblotting, and other standard molecular biology assays.

Saliva will be collected at study assessment visits in a 15mL sterilized tube; roughly 3mL. Once collected, saliva will be immediately placed on ice and stored at -80 degrees until subsequent analysis.

The procedure below describes the blood and saliva collection timeline during the 12-week intervention period for both intervention groups:

*Week 1:* Taken immediately prior to exercise, immediately post, 15 min post, 30 min post.

*Week 6:* Taken immediately prior to exercise, immediately post, 15 min post, 30 min post.

*Week 12:* Taken immediately prior to exercise, immediately post, 15 min post, 30 min post.

All blood draws will be conducted at the Atlanta VA Health Care System. Tubes will be coded and thus have no identifiable patient information. It is expected that all blood sample processing and storing will be conducted at the Atlanta VAHCS in the Molecular Core facility. However, in the event that equipment or other resources are needed for completing sample analysis, samples will be analyzed at Emory University (5th Floor, Emory Eye Center, Clinic Building B, [name]). Sample labels will be de-identified by having only Subject #, Visit #, Draw #. The master code list will be maintained in a locked file cabinet in the Atlanta VAHCS office of the PI or Coinvestigator. Deidentified sample remainders will be kept at the Atlanta VA Core facility or, if needed, the Emory facility, while the study remains open.

#### Finger prick blood measurements

Similar to a glucose meter, a hematocrit (Hct) meter requires a very small droplet of blood to measure hemoglobin and Hct using a photometer with broad spectrum. We will use an analyzer called the HemoPoint H2 from StanBio Laboratory. This device is a palm-sized blood hematocrit test meter that quickly measures hemoglobin and Hct from a small blood sampling (0.3µl). Measurements are completed in 30 sec, so this measurement can be completed rapidly and repeatedly within a single session. Prior to each puncture, we will cleanse the target skin site with an alcohol swab. We will use a 28 or 30G lancet to draw a droplet of blood into a measurement strip for each measurement. After recording the data, we will discard the lancet and the lactate strip into a Sharps container for safe disposal. We will apply direct pressure to the site of puncture with a sterile gauze pad. The puncture procedure will attempt to minimize pain and discomfort for the participants. The Hct measures will be utilized along with MRI-based pCASL measures to accurately quantify the subject's CBF.

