### **Statistical Analysis for Specific Aim 2**

Specific Aim 2 is to determine the impact of an aerobic intervention on CVR. Similar to Aim 1, we will test each BOLD change value jointly using a linear mixed-effects model to determine whether the mean change of the groups is significantly different across the time points (Pre and Post). Fixed effect will be group (Spin vs Control) and the random effect will be time (Pre vs Post). Additional analyses will use multiple regressions to describe the effect by participant demographics (gender, race, age, and hypertensive status) or by MoCA score. An FDR of  $q = 0.05$  will be calculated and used to correct for multiple test and effect sizes will be computed.

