### **Statistical Analysis for Specific Aim 3**

The task fMRI BOLD images will be processed for slice-timing correction, and each image volume will be corrected for rigid-body head motion. The volume registered images will be inspected for artifacts induced by motion, cardiac pulsation and respiratory cycles and removed spatio-temporally using Independent Component Analysis (ICA). These artifact-free images will then be spatially transformed to MNI space using linear and non-linear co-registration algorithms. Following this spatial transformation, the images will be smoothed within the brain to increase the signal-to-noise ratio. Then the images will be scaled to accurately determine the relative percent signal change in BOLD induced by the task. Finally, task-induced BOLD changes ( $\Delta$ BOLD) from pre- to post-aerobic intervention and corresponding hemodynamic response functions are quantified using deconvolution technique.

Since the goal of this aim is to quantify the impact of baseline physiologic measures (ie, resting blood flow and CVR) on task-induced BOLD changes, we plan to accomplish this task by modeling the contributions of perfusion and CVR to  $\Delta$ BOLD responses. The equations below describe our simple modeling approach using linear regression:

$$\Delta BOLD_{i,ROI} = A + B \cdot CBF_{i,ROI} + C \cdot CVR_{i,ROI} + D \cdot (CBF_{i,ROI} \times CVR_{i,ROI})$$

Where subscript  $i$ =pre or post session, ROI refers to the regions of interest, and coefficients A is the modeled intercept, B and C are modeled slopes for perfusion and CVR contributions, and D is modeled slope for the interaction between perfusion and CVR respectively. We will compare the slopes obtained for pre and post exercise to explore (a) how each of the baseline measures (ie, perfusion and CVR) change in response to exercise, and (b) within each condition (pre or post), disentangle perfusion and vascular influence on task-induced BOLD change. Also, modeling for the interaction will account for the coupling effect which by itself can provide insightful information in terms of exercise-induced perfusion-CVR coupled effects. We plan to carry out the

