above processing and modeling at the ROI level as it renders more detection power and is computationally less intensive. From a statistical standpoint, we will compute the F score to test the significance of overall fitting of the model, and we will also obtain the  $t$  score for each predictor (perfusion and CVR) to test the significance of their association with change in measured variable ( $\Delta$ BOLD). To evaluate responsiveness to training and its impact on the model, post hoc analysis will include stepwise multiple regression to evaluate delta VO2 on perfusion and CVR in a-priori ROIs as well as behavioral outcomes.

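### Hematocrit is measured but used only for CBF; Aim 3 omits it although it can drive both BOLD-based CVR and task BOLD, so the variance credited to CVR may be inflated

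*Combined protocol and SAP*

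**What the plan says.** All references are to the combined protocol and SAP.

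- **Finger prick blood measurements.** One use of hematocrit is named: "The Hct measures will be utilized along with MRI-based pCASL measures to accurately quantify" CBF. The reading is quick and repeatable ("Measurements are completed in 30 sec, so this measurement can be completed rapidly and repeatedly within a single session"), but the section does not tie it to a particular visit.
- **Statistical Analysis for Specific Aim 2.** CVR enters as a BOLD measure: "we will test each BOLD change value jointly using a linear mixed-effects model". The secondary regressions do not include hematocrit: "Additional analyses will use multiple regressions to describe the effect by participant demographics (gender, race, age, and hypertensive status) or by MoCA score".
- **Statistical Analysis for Specific Aim 3.** The stated approach is "we plan to accomplish this task by modeling the contributions of perfusion and CVR to" the task BOLD response, by region and separately before and after the intervention. Of the coefficients, "B and C are modeled slopes for perfusion and CVR contributions, and D is modeled slope for the interaction between perfusion and CVR"; the only other one is the intercept. For inference, "we will compute the F score to test the significance of overall fitting of the model", with a t score for perfusion and for CVR.
- **Power Analysis and Sample Size.** For Aim 3, 88 participants, alpha 0.05 and power 0.80 are said to detect an R² increase of 0.111 per region.

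No section corrects CVR or task BOLD for hematocrit, adjusts for it, or plans a sensitivity analysis on it.

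**The concern.** BOLD contrast comes from deoxyhemoglobin. For the same vascular or neural response, a person with more hemoglobin can show a larger BOLD change, both under CO₂ (the CVR predictor) and during the task (the outcome). Hematocrit is then a common cause of a predictor and the outcome, and the model leaves it out although the trial measures it.

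Aim 3 asks how much task-BOLD variance perfusion and CVR explain. The Background section gives the purpose as separating vascular function from baseline neural activity. Hematocrit is neither, but variance it produces in both BOLD measures would be booked to CVR. At stake are the overall F test, the CVR t test and the reported R².

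**Working it through.** **Inputs from the documents:** N = 88, alpha 0.05, detectable R² 0.111, three predictors (CBF, CVR, CBF × CVR). **Assumptions, not in the documents:** every hematocrit correlation, mean, SD, exponent and CV below.

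**1. The plan's own figure.** With f² = R²/(1 − R²) = 0.111/0.889 = 0.125 and noncentrality λ = 88 × f² = 10.99, the F test on 3 and 84 degrees of freedom has power 0.783. The R² detectable at power 0.80 is 0.115. The stated 0.111 is therefore reproduced closely if three terms are tested.

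**2. R² from shared hematocrit alone.** Let hematocrit correlate r with CVR and with task BOLD, and c with CBF, with no other link among them.

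- If c = 0, R² = r⁴.
- If c = −r, R² = 2r⁴/(1 + r²).

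**3. Rejection at nominal 5%** (10,000 simulated trials per row, N = 88):

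| r | c | shared R² | F | CBF t | CVR t | F, hematocrit in model |
|---|---|---|---|---|---|---|
| 0 | 0 | 0 | 4.8% | 5.1% | 4.9% | – |
| 0.2 | 0 | 0.002 | 6.0% | 4.8% | 6.6% | 4.9% |
| 0.2 | −0.2 | 0.003 | 6.8% | 5.9% | 6.6% | 5.1% |
| 0.3 | 0 | 0.008 | 9.5% | 4.9% | 12.6% | 4.9% |
| 0.3 | −0.3 | 0.015 | 13.0% | 11.6% | 11.0% | 5.0% |
| 0.4 | 0 | 0.026 | 20.9% | 4.9% | 30.9% | 5.0% |
| 0.4 | −0.4 | 0.044 | 34.7% | 24.1% | 24.3% | 4.8% |
| 0.5 | 0 | 0.063 | 48.0% | 5.2% | 63.2% | 5.0% |
| 0.5 | −0.5 | 0.100 | 72.1% | 46.1% | 44.8% | 5.4% |

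The perfusion t test stays near 5% whenever CBF is unrelated to hematocrit. The CVR t test does not need that link to be inflated.

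**4. What r might be.** Assume BOLD and CVR proportional to hematocrit, hematocrit mean 0.42 with SD 0.03–0.04, CBF proportional to hematocrit to the power −0.5 to −1, and one common CV v for all other between-person variation. With q = SD/mean = 0.0714 to 0.0952, r ≈ q/√(q² + v² + q²v²).

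| v | r | F rejects, no true link |
|---|---|---|
| 35% | 0.20–0.26 | about 6–10% |
| 25% | 0.27–0.35 | about 8–24% |
| 15% | 0.43–0.53 | about 30–84% |

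Repeat simulations put the upper end at v = 25% between 21% and 24%. If CBF is made independent of hematocrit, the whole grid runs from about 6% to 62%.

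**5. Against the plan's 0.111.** Through CVR alone, r⁴ = 0.111 needs r = 0.58. If CBF shares the factor equally, 2r⁴/(1 + r²) = 0.111 needs r ≈ 0.51. Only the strongest cell in step 4 reaches that: r = 0.53 gives 2 × 0.0789/1.281 = 0.123.

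**6. With hematocrit in the model.** Rejection returns to about 5% if the reading is error-free. In the strongest cell, an assumed reading error of SD 0.02 leaves about 11%, and SD 0.03 about 23%.

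**The case against.** **The mechanism and its size are not in the documents.** The Background attributes BOLD to flow and metabolism and does not mention hematocrit. Deoxyhemoglobin physics supports a direction, but not strict proportionality or any particular CV, and the CV largely decides the answer. At r = 0.2 the inflation is 1 to 2 percentage points. This stands, and it is why only a range can be given.

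**A zero-link null is not the trial's question.** Aim 3 presumes that baseline physiology matters and asks how much. If people differ in flow because they differ in hematocrit, that is a real perfusion difference, and adjustment removes part of it. This also stands. It argues for reporting both R² values, not for leaving hematocrit out.

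**CBF is already handled.** Hematocrit is paired with pCASL quantification. A reader might infer that the perfusion term is distorted as well; that follows only if corrected CBF still varies with hematocrit, which the documents do not say.

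**CVR may not be purely BOLD-based.** The MRI section describes the CO₂ challenge in its blood-flow imaging paragraph. The BOLD reading rests on the Aim 2 analysis section, which is explicit. If CVR were derived from flow imaging instead, the shared route would be weaker.

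**Aim 2.** A reader might infer that training lowers hematocrit and so biases the between-arm CVR comparison. The documents report no hematocrit change by arm and no such training effect. Post-intervention hematocrit is also measured after randomization and may be affected by training, so adjusting for it is not neutral.

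**Conclusion.** The point holds for Aim 3, mainly through CVR. A measured variable that can drive both BOLD-based CVR and task BOLD is missing from the regression, so the F test, the CVR t test and the R² credited to CVR can be too favorable. The size is unknown: under the stated assumptions, the false-positive rate of the nominal 5% F test runs from about 6% to about 84%, depending chiefly on the other between-person variation.

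A reader might conclude that a positive Aim 3 result would be hematocrit and nothing else. The documents do not support that. For correlations up to 0.5, the R² produced by hematocrit alone stays below the plan's 0.111, and only the strongest assumed cell exceeds it. The risk is false significance and a biased variance share, which the data as currently analyzed could not reveal.

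**What to change.** **Aim 3.**

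- State that the finger-prick reading is taken at each MRI session.
- Add same-session hematocrit as a covariate in the pre and post regressions.
- Report the R² that perfusion and CVR add over hematocrit alone, beside the unadjusted R².
- Write this in before analysis, so that it does not look post hoc.

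**Aim 2.** Keep the unadjusted Spin-versus-Control comparison as primary. Report the hematocrit-adjusted CVR change only as a sensitivity analysis, noting that post-intervention hematocrit may itself respond to training.

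**Cost.** The device and the measurement are already in the protocol. The covariate takes one degree of freedom (error df 84 to 83). With 88 participants, power at R² = 0.111 stays at 0.783 and the detectable R² at 0.115, both to three decimals. The R² credited to perfusion and CVR may fall. There is some over-adjustment if hematocrit acts on BOLD through real flow differences, and correction is incomplete if the reading is noisy. Repeat readings within a session, which the device allows, would reduce the noise.

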#### **Interventions**

*Aerobic Exercise Group:* For this arm of intervention, randomized participants will attend spin exercise training sessions demonstrated to facilitate physiological changes. For the

aerobic exercise component of this group, participants will follow the guidelines provided by the American College of Sports Medicine for optimizing cardiovascular fitness. Thus, participants will exercise 3 times a week on a stationary ergometer. Exercise intensity will begin at low levels (50% of maximal heart rate reserve) calculated utilizing the Karvonen method. Briefly, target exercise HR is calculated by subtracting the persons age from 220. Resting heart rate is then subtracted from this number. The answer is then multiplied by the target percent (50% for example) and the product is added back to resting heart rate to provide the target exercise session heart rate. Intensity will be increased by 5% every week (as tolerated by the participant) to a maximum of 90% of maximal heart rate. Exercise time will progress from an initial 25 minutes per session to a maximum of 60 minutes by increasing 5 minutes each week. Each session will be monitored by a certified CPR and fitness specialist. Further, the intervention site is located in the Atlanta VA Health Care System and portable defibrillators are available at the intervention site.

*Interval Exercise Group:* For 12-weeks participants will engage in progressive whole body stretching, toning and balance exercises designed for individuals 65 years and older. Participants will meet for the same total duration time as the aerobic exercise group. Heart rate will be monitored to ensure participants maintain exercise levels below aerobic training zone.

*Remote Exercise Monitoring:* As an alternative, participants that are uncomfortable with receiving face-to-face training within the hospital will be given the option to continue their exercise intervention visits remotely. For participants that have been randomly assigned to the 'spin' exercise training program, will be provided a stationary cycle ergometer that has been sanitized properly to use during the 12-week period. All subjects will be monitored and trained through VA and Emory approved remote access sites.

*Control Group:* A random subset of participants will be in a 12-week wait-list control. These participants will undergo the same scanning procedures as described above without cognitive or physical function testing. After 12-weeks these participants will come in and undergo the pre-assessment, 12-week exercise intervention and post assessment as described above.

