## **7. Statistical Analysis:**

### **Statistical Analysis for Specific Aim 1**

Specific Aim 1 is to determine whether there will be a statistically significant difference in the cerebral perfusion data between the two groups (Spin and Control) following the intervention. We will assess the perfusion values jointly using a linear mixed-effects model to determine whether the mean change in perfusion between the groups is significantly different. For the model the fixed effect will be group (Spin vs Control) and the random effect will be time (Pre vs Post). We expect that modeling the outcomes jointly will increase the statistical power. This model will enable us to estimate the

overall effects of time and the interventions, and most importantly, how the effects of the interventions differ with time. Additional analyses will use multiple regressions to describe the effect of participant demographics such as gender, race, age, hypertensive status as well as MoCA score. A false discovery rate (FDR) of  $q = 0.05$  will be calculated and used to correct for multiple tests and effect sizes will be computed.

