For behavioral data, we estimate the effect size for semantic fluency from 2 sources of data using the same treatment we will use for this study. For our lab the effect size for change in the Spin group was  $d=1.804$ , and for the preliminary data from an ongoing study the effect size for change in semantic fluency was  $d=1.410$ . Using the more conservative of the two estimates,  $n=44$  and a FDR corrected  $\alpha=0.0261$ , power approaches 1.00. Again, an effect size of  $d=0.5$  would achieve a power of 0.80, which seems quite achievable given the large effect sizes in two independent samples. Use of the Control in this instance is problematic because of a large negative outlier, yielding a large negative mean (-2.000, indicating a loss of semantic fluency) and a large standard deviation. Even so, these data yield an effect size of  $d=0.886$ , but these data are not stable enough to yield a good estimate of between-group effect size. With  $n=44$  per group and  $\alpha=.05$  (FDR corrected), an effect size of  $d=0.64$  would yield a power of 0.80. Based on the strong effect size for Spin, we believe this is an achievable effect size for a between-group analysis based on what we know about the Spin intervention.

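### If Control means the wait-list arm, the sized fluency comparison has no unexercised control data, and the plan does not say which wait-list scans are Pre and Post

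*Combined protocol and SAP*

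**What the plan says.** **Wait-list arm.** In section 5, Interventions, the paragraph headed Control Group begins "A random subset of participants will be in a 12-week wait-list control". The size of the subset is not given. It continues: "These participants will undergo the same scanning procedures as described above without cognitive or physical function testing". After the wait: "After 12-weeks these participants will come in and undergo the pre-assessment, 12-week exercise intervention and post assessment as described above". The type of exercise is not named.

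**Scan times.** The general rule under FMRI Tasks is "Participants will be scanned prior to and following the 12-week intervention". No number or timing of scans is given for the wait itself.

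**Analysis.** For Aim 1, section 7 states "For the model the fixed effect will be group (Spin vs Control) and the random effect will be time (Pre vs Post"), and Aim 2 uses the same two factors. Neither defines Pre and Post for someone who waits and then exercises. Behavioral and Self-Report Data plans paired pre/post t-tests for fluency and motor skills and a mixed regression on session. Power Analysis and Sample Size gives a between-group fluency calculation (44 per group, d = 0.64, power 0.80) and says of that d: "we believe this is an achievable effect size for a between-group analysis".

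**Which arm is Control.** Specific Aims has two arms, aerobic and stretching, and the Aim 1 hypothesis describes Control as a non-aerobic intervention. Participant selection has three arms, with Control separate from Interval Exercise. Interventions puts the stretching programme under the Interval Exercise name and the wait-list under the Control name.

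**The concern.** A control arm should show what happens over 12 weeks without the intervention. For tests given outside the scanner, the wait-list arm cannot do so: nothing is measured while its members wait, and what is measured later spans an exercise programme. A wait-list pre/post change in fluency, physical function or treadmill VO2 is thus a change with exercise.

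For imaging the needed data appear to be collected, but no rule selects them. A wait-list participant may have a waiting interval and an exercise interval. An analyst who follows the labels in the Control Group paragraph would take the second as Pre and Post, and the contrast would compare exercise with exercise. An analyst who adds the second interval to Spin would put one person in both groups, with data that are neither randomised nor concurrent. An analyst who uses the waiting interval gets the intended contrast. The plan does not choose among these, so the choice could be made after the data are seen.

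The same gap touches the post hoc regression in Aim 3 that relates change in VO2 to perfusion, CVR and behaviour. For this arm a treadmill VO2 change exists only over the exercise period, so pairing it with a waiting-period perfusion change would mix intervals.

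**Working it through.** **Step 1. What exists for a wait-list participant, by period.**

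| Measure | During the wait | Around the later exercise |
|---|---|---|
| Perfusion and CVR scans | Yes; number and times not stated | Yes, if the assessments described earlier include scans |
| Out-of-scanner cognitive tests, including fluency | No | Yes |
| Physical function, including treadmill testing (item 8 in that list) | No | Yes |
| Motor tests (own heading) | Not expressly excluded | Yes |
| Visits labelled pre and post | None | Both |

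**Step 2. Reproduce the plan's figure.** Inputs from Power Analysis and Sample Size: n = 44 per group, d = 0.64, power 0.80. Alpha is written as .05 (FDR corrected) for this comparison and as 0.0261 elsewhere in the section. Sidedness is not stated; two-sided is assumed.

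Noncentrality = d × √(n/2) = 0.64 × √22 = 3.00, with 2n − 2 = 86 degrees of freedom.

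- Alpha 0.0261: power 0.781 by the normal approximation, 0.768 by noncentral t.
- Alpha .05: power 0.851 normal, 0.843 noncentral t.

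The stated 0.80 is reproduced to within two points by the normal approximation at 0.0261. The figure itself is not in dispute.

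**Step 3. Illustrate the consequence.** Let the average Control change be a fraction c of the Spin effect, with the standard deviation unchanged. The expected difference is d = 0.64 × (1 − c). If every Control record brackets exercise, c is the post-wait exercise effect relative to Spin. If only some do and the effects are equal, c is the fraction of records that do. Noncentral t, two-sided, 44 per group:

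| c | d | Power, alpha .05 | Power, alpha 0.0261 |
|---|---|---|---|
| 0 | 0.64 | 0.843 | 0.768 |
| 1/4 | 0.48 | 0.605 | 0.498 |
| 1/3 | 0.43 | 0.508 | 0.400 |
| 1/2 | 0.32 | 0.317 | 0.228 |
| 3/4 | 0.16 | 0.115 | 0.070 |
| 1 | 0 | 0.050 | 0.026 |

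The documents give no value for c: neither the size of the wait-list subset nor the type of exercise after the wait is stated. The table shows a range and is not a forecast.

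**Step 4. The n per group.** If the 108 completers were all older adults split equally over three arms (an assumption), each arm would have 108/3 = 36. At d = 0.64, noncentral t power is then 0.764 at alpha .05 and 0.671 at 0.0261, and 0.80 at 0.0261 would need d = 0.74.

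**The case against.** **The wait-list is scanned while waiting.** A reader might infer that any Control pre/post change, including perfusion and CVR, measures exercise. The documents do not support that. The sentence before the crossover gives these participants the same scanning procedures, and perfusion and CVR come from scans. If scans fall at both ends of the wait, a no-exercise change is available. Nothing says that post-switch scans carry the Control label or are pooled into Spin. The imaging defect is an undefined mapping, not shown contamination.

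**Not all behavioural data are absent.** Motor tests are not expressly excluded during the wait, and the fluency task in the scanner might yield some responses. So the wait-list cannot be said to have no unexercised behavioural data at all. The gap is confined to out-of-scanner cognitive tests and physical function.

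**Control may mean stretching.** Specific Aims reads that way, and the power section describes earlier Control fluency data, so that Control group was cognitively tested. On this reading the planned contrasts are intact. The sizes do not settle the matter: 2 × 44 = 88, the number used for Aim 3, and the other 108 − 88 = 20 completers are assigned to no group. Against this reading, the arm names in Interventions and Participant selection give Control to the wait-list. The objection limits the point's reach but does not remove the need for a statement.

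**The behavioural analysis section names no Control contrast.** True: it plans paired tests. But the power section sizes a between-group fluency analysis and calls its effect size achievable, so one is evidently intended.

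**The later exercise need not be Spin.** Also true. If it were the stretching programme, c could be well below 1. The wait-list would then act as a delayed stretching group, which is still not an unexercised control and is not concurrent with Spin.

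**Conclusion.** The point holds in two parts.

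1. **Behaviour and fitness.** If section 7's Control is the arm that Interventions and Participant selection call Control, the fluency comparison sized at 44 per group has no unexercised out-of-scanner control data, and a wait-list pre/post change in fluency, physical function or treadmill VO2 is an exercise change. This follows from the text without calculation. If Control means stretching, the comparison stands, but the plan must say so.
2. **Imaging, Aims 1 and 2.** A no-exercise change can probably be formed, provided scans are taken at both ends of the wait. The plan does not name those scans as the Control Pre and Post and does not keep post-switch data out of the contrast.

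The size cannot be fixed from the documents. The power losses in the table rest on an assumed c, an unchanged standard deviation and the fluency effect size of 0.64; they should not be carried over to perfusion or CVR. The matter should be settled before analysis, because the group contrast is the question in Aims 1 and 2 and the possible readings give results with different meanings.

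**What to change.** - **Name the arms once.** Reconcile Specific Aims, Interventions, Participant selection, the Aim 1 and Aim 2 analyses, Behavioral and Self-Report Data, and Power Analysis and Sample Size on how many arms there are and which one is Control.
- **Fix the imaging window.** State that the randomised comparison uses only scans from the first 12 weeks after randomisation; for wait-list participants these are the scans at the start and end of the wait. Give those scan times in the Control Group paragraph.
- **Rule on post-switch data.** State that they enter neither group in that comparison and are reported only as a separate, uncontrolled within-person result.
- **Limit the behavioural role of the wait-list.** State that it supplies no control data for out-of-scanner cognitive tests, physical function or VO2. Take any between-group comparison of these against the concurrently tested stretching arm.
- **Restate n per group and power** for the arms actually compared.

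**Cost.** The change is wording, with no new visits if scans at both ends of the wait are already scheduled; the sponsor should confirm that. The downside is that the behavioural Control n may be smaller than 44, with lower power than stated.
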